12.5. Laboratory data

Exhibit 2 – Exhibit 7 displays the timing of laboratory tests. Clinical laboratory values and

changes from baseline will be summarized by study part, treatment group and time point.

Laboratory data will be summarized by presenting shift tables from baseline to each post-

baseline time point. Figures may be used if appropriate.

12.6.Audiologic evaluation

Audiologic evaluations were used as exploratory clinical endpoints as well as additional safety

measurements assessing ototoxicity. The audiologic evaluations performed over the course of

the study included: behavioral assessment of pure tones and speech measures (threshold and

word discrimination), tympanometry, otoacoustic emissions, and ABR. Pure tone assessment

(Air Conduction and Bone Conduction) will be summarized as it best captures possible

ototoxicity.

Air conduction (AC) was tested at the following frequencies: 250 Hz, 500 Hz, 1000 Hz,

2000 Hz, 3000 Hz, 4000 Hz, 6000 Hz, and 8000 Hz. Bone conduction (BC) was tested at the

following frequencies: 250 Hz, 500 Hz, 1000 Hz, 2000 Hz, and 4000 Hz. Descriptive statistics

of hearing thresholds in decibels will be presented by study part, treatment group, conduction

type, visit, frequency and ear.

Pure tone averaging was done for both AC and BC across low frequencies of 500 Hz, 1000 Hz,

and 2000 Hz. Pure tone averaging will also be done for AC at high frequencies of 4000 Hz,

6000 Hz, and 8000 Hz. If at least two non-missing thresholds are obtained per conduction type

and ear, the pure tone average (PTA) for AC and the bone conduction average (BCA) for BC

will be calculated by adding up the threshold levels in decibels (dB), and then dividing the

sum by the number of thresholds obtained. PTA and BCA will be summarized by study part,

treatment group, visit and ear.

CONFIDENTIAL

August 27, 2018

Page 44

A diagnostic ABR was tested at the following frequencies: 500 Hz, 1000 Hz, 2000 Hz, and 4000 Hz. Descriptive statistics of hearing thresholds in decibels will be presented by study part, treatment group, visit, frequency and ear.

When conducting the PTA and ABR, the sites recorded the type of hearing impairment and hearing impairment severity. Hearing impairment severity was categorized as follows (more than one could apply to a subject at each assessment).

- Normal hearing (-10 to 15 dB)
- Slight hearing impairment (16 to 25 dB)
- Mild hearing impairment (26 to 40 dB)

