- Moderate hearing impairment (41 to 55 dB)
- Moderate-severe hearing impairment (56 to 70dB)
- Severe hearing impairment (71 to 90 dB)
- Profound hearing impairment (91 + dB)
- High Frequency Hearing Impairment (defined as an impairment at 4k and above)

Hearing impairment severity will be summarized for both PTA and ABR by study part, treatment group and visit.

All audiometry assessments will be listed by subject.

A sensitivity analysis will be performed to address the impact that the known risk of ototoxicity from study drug may have on the adequacy of blinding. The concern comes if the site staff performing the NPC-SS assessment notices over the course of the study that the subject experiences clinical hearing impairment. Will the knowledge of hearing impairment cause the NPC-SS assessment to be knowingly or unknowingly biased? Because the audiologic evaluation results are kept blinded from the site staff performing the NPC-SS assessment, we will instead use the reporting of hearing impairment as an adverse event (by the blinded AE rater) due to clinical manifestation as a marker of hearing impairment in this analysis. A standard MedDRA query for hearing impairment will be used to identify these terms. The recommendation for hearing aides to a subject will also be included in this

analysis. The site staff member performing the NPC-SS assessment also is blinded to the AEs

that are recorded for the subject.

In order to assess whether there was an impact due to unblinding, the co-primary efficacy

NPC-SS composite endpoint analysis will be repeated (a nonparametric ANCOVA, with

treatment group, study part, and baseline included in the model), but will also include a

variable indicating the recording of hearing impairment (AE or recommendation for hearing

aid) and a hearing impairment by treatment group interaction variable in the model. A

significant hearing impairment by treatment group interaction variable (two-sided α =0.05 level

of significance) will provide evidence that an unblinding bias has occurred.

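### The pure tone and bone conduction averages use whichever frequencies were obtained, so a change in the set of frequencies can shift the average in either direction without any change in hearing

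*SAP*

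**What the plan says.** SAP 12.6 defines two frequency bands. For the low band: "Pure tone averaging was done for both AC and BC across low frequencies of 500 Hz, 1000 Hz" and 2000 Hz. For the high band: "Pure tone averaging will also be done for AC at high frequencies of 4000 Hz", 6000 Hz and 8000 Hz. The condition for computing an average is "If at least two non-missing thresholds are obtained per conduction type" and ear. The levels are added and the rule divides the "sum by the number of thresholds obtained". On reporting, "PTA and BCA will be summarized by study part", treatment group, visit and ear.

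Section 12.6 is silent on four points:

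- whether the frequencies averaged at a visit must match those averaged at baseline;
- whether the minimum of two applies within each band;
- how a tone with no response is coded;
- whether change from baseline is summarised. It is stated for vital signs (SAP 12.3) and laboratory values (SAP 12.5), but not for thresholds or their averages.

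The averages are not the only hearing output. SAP 12.6 also describes individual thresholds by conduction "type, visit, frequency and ear", summarises severity categories including one for impairment at 4 kHz and above, and lists all audiometry. SAP 12.1.1 grades hearing adverse events from threshold shifts at named frequencies, and SAP 12.1.2 tabulates hearing impairment as an event of special interest.

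**The concern.** An average is comparable between visits only if it covers the same frequencies. Under this rule an ear can contribute 4, 6 and 8 kHz at baseline and only 4 and 6 kHz later. If thresholds differ across frequencies, the average then moves because its composition changed.

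The wording of the minimum adds to this. Read literally, an ear with air-conduction thresholds at 500 and 8000 Hz only has its two thresholds for that conduction type, yet each band holds a single value.

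The SAP treats hearing as a recognised harm: "A sensitivity analysis will be performed to address the impact that the known risk of ototoxicity from study drug" may have on blinding. Bone conduction and diagnostic ABR stop at 4000 Hz, so the high-frequency air-conduction average is the only planned average that reaches 6 and 8 kHz. Incomplete audiograms are plausible: the Protocol synopsis admits children from 4 years of age with cognition scores up to 4, and SAP 12.1.1 provides for cases where behavioural audiometry cannot be obtained. Groups are small (35 and 16 planned, three sham subjects in Part A, SAP Exhibit 1) and tables are split by part and ear, so a few ears can move a mean.

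**Working it through.** The documents give no average, missing rate or expected shift, so there is no planned figure to reproduce. The check applies the SAP's rule to assumed audiograms. T4, T6 and T8 are the thresholds in dB at 4, 6 and 8 kHz.

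**Formula.** With all three, the average is (T4 + T6 + T8)/3. Without 8 kHz it is (T4 + T6)/2. The difference is (T8 − mean(T4, T6))/3, so the average falls only if 8 kHz is worse than the mean of the other two. Likewise, losing 4 kHz raises the average by (mean(T6, T8) − T4)/3 when 4 kHz is the better threshold.

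**Size per ear** (assumed excess of 8 kHz over the mean of 4 and 6 kHz):

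- 10 dB: 10/3 = 3.3 dB
- 25 dB: 25/3 = 8.3 dB
- 40 dB: 40/3 = 13.3 dB

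**Direction, with no true change in hearing:**

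- 15/25/35 dB: full average 25. Without 8 kHz, 20 (−5). Without 4 kHz, 30 (+5).
- Reverse slope 35/25/15 dB: full average 25. Without 8 kHz, 30 (+5).

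**With a true change:**

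- Baseline 15/25/35, +25 dB at every frequency: true shift +25. Without 8 kHz the visit average is 45, an apparent +20. On common frequencies, (40 + 50)/2 − (15 + 25)/2 = +25.
- Flat baseline of 15, +25 dB at every frequency: +25 with or without 8 kHz, so no distortion.
- Flat baseline of 15, +25 dB at 8 kHz only: true three-frequency shift 23.3 − 15 = +8.3. Without 8 kHz, 0. Matching frequencies also gives 0.
- Baseline 40/60/85, later 50/75 with 8 kHz not obtained: 185/3 = 61.7 and 125/2 = 62.5, an apparent +0.8. On common frequencies, 62.5 − 50.0 = +12.5.

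**Group mean.** The understatement is the share of ears losing 8 kHz times the per-ear drop. For assumed shares of 5% to 30% and an excess of 10 to 40 dB, it runs from 0.05 × 3.3 = 0.2 dB to 0.30 × 13.3 = 4.0 dB. This takes baseline as complete. In a three-subject group, one ear losing 8 kHz with a 25 dB excess moves that ear's mean by 8.3/3 = 2.8 dB.

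**The case against.** The strongest reply is that the average is one derived, descriptive summary among several, with no test or decision rule attached. In the 40/60/85 example the by-frequency tables would carry the move from 40 to 50 dB at 4 kHz and from 60 to 75 dB at 6 kHz, which is the +12.5 dB that the average misses. Adverse-event grades rest on shifts at named frequencies and do not use the average. Severity categories and full listings remain. An absent 8 kHz value is also a limit of the data, which no averaging rule can cure.

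Most of this stands and fixes the scope of the point. It does not make the average sound. In the same example the shifts of 10 and 15 dB do not exceed the 20 dB grading criterion, and the 8 kHz shift cannot be graded. The 8 kHz table mean loses that ear too. A reader of the average would still see almost no change.

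Two stronger readings are tempting. A reader might infer that losing the top frequency always lowers the average and so conceals ototoxicity; the flat and reverse-slope cases show that this is not general, and the other outputs remain. A reader might also infer that thresholds go missing because hearing has become too poor to measure, more often on VTS-270. The documents give neither the rate nor the cause of missing thresholds, nor how a no-response is stored.

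**Conclusion.** The point holds as a limited defect in a descriptive safety summary. The rule lets the averaged frequencies differ between a subject's visits, and on a sloping audiogram this alone moves the high-frequency average by an assumed 3.3 to 13.3 dB per ear when 8 kHz is lost. The sign depends on the audiogram's shape and on which frequency is lost, so change can be understated or overstated. The same mechanism applies to the low-band averages if thresholds differ across 500 to 2000 Hz.

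The sizes rest on assumed slopes; the group-mean range of 0.2 to 4.0 dB also rests on assumed missing rates. The documents do not support saying that the plan as a whole hides ototoxicity, or that the comparison of VTS-270 with sham is biased in a known direction.

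**What to change.** In SAP 12.6:

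1. Apply the minimum of two thresholds within each band, for each conduction type and ear.
2. Summarise change from baseline in the low- and high-frequency averages by treatment group and visit, using only the frequencies measured in that ear at both baseline and the visit.
3. Show the number of ears available at each frequency and visit.
4. Where the data record a no-response separately from a test not done, report it as such and do not treat it as simply missing. No numerical substitute is proposed, because the documents give no audiometer limits to base one on.

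The cost of items 1 to 3 is SAP wording and programming on thresholds the trial already collects; item 2 adds a summary. Item 4 depends on what the case report form holds, which the documents do not show. The downsides are slightly less precision when only two frequencies are common, and that a loss confined to 8 kHz still cannot be recovered from the average when 8 kHz was not obtained. The counts in item 3 at least make that gap visible.

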8.5. Sample size determination and power calculation

The sample size for this study is approximately 51 subjects in Parts A and B combined. The

rationale for the sample was based on both clinical and statistical considerations. Based on

the comparison of the NIH phase 1 subjects and similar subjects in the NIH natural history dataset, approximately 51 subjects: 16 on sham and 35 on active treatment will allow for the detection of a clinically relevant difference of the sum of the 4 NPC-SS domains that make up the composite outcome.

The power calculation was based on the primary endpoint, defined as the change from baseline at week 52 in the VTS-270 group compared to the sham group in the composite outcome that is the sum of the ambulation, cognition, fine motor, and swallowing scores of the NPC-SS. This outcome ranges between 0 and 20 at each assessment. Positive values for this change indicate a decline in function whereas negative values indicate improvement. The assumptions for the calculation of the power are as follows:

- The VTS-270 group has an average increase in value over 52 weeks ranging from 0 points to 0.2 points. Taking the greatest decline of this range, the estimate of (composite outcome at week 52) (composite outcome at baseline) = 0.2
- The sham group has an average increase in value over 52 weeks ranging from 1.6 points to 1.9 points. Taking the least decline of this range, the estimate of (composite outcome at week 52) (composite outcome at baseline) = 1.6.
- A common standard deviation of 1.64.
- The sample size in the VTS-270 group is 35 and the sample size in the sham group is 16.
- Two-sided alpha = 0.05.

Based on these assumptions, an analysis of covariance (ANCOVA) will have 79% power to detect a statistically significant difference between the VTS-270 and sham groups.

Three additional subjects above the planned sample size were enrolled into the study, such that there were 54 subjects randomized. Assuming a 5-10% drop out rate, the number of completers could range from 48-51. Thus, the power of the trial, based on the parameters above, could range from 76% if 48 subjects complete to 79% if 51 subjects complete.

Six different scenarios are presented in Table 1. These are various differences based on an assumed average increase of 0 to 0.2 points in the composite outcome in the VTS-270 group

August 27, 2018 Page 26

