over a 12-month period and an average increase in the composite outcome ranging from 1.6 to 1.9 points in the sham group. Thus, the difference in the change from baseline to 52 weeks for the two groups ranges from 1.4 to 1.9 (this is based on 1.6 - 0.2 and 1.9 - 0). In general, the study is well-powered to detect differences that are similar to those that were observed between the Phase 1/2a and natural history study with the power for the scenarios presented below ranging from 0.79 to 0.96.

Table 1. Estimated power for the VTS301 protocol where VTS-270 group is assumed to increase 0 to 0.2 points over 1 year

Estimated difference in change from baseline for the VTS-270 group compared to sham

1.9 points

1.8 points

1.7 points

1.6 points

1.6 points

1.5 points

1.5 points

1.5 points

1.6 points

1.7 points

1.8 points

1.9 points

1.8 points

1.8 points

1.9 points

1.8 points

1.9 points

1.8 points

1.9 points

0.79

No formal power calculation was performed for clinician CGIC.

8.6.Pooling of investigator sites

1.4 points

Analyses will not be stratified by site since the study has many investigative sites (20) relative to the anticipated number of randomized subjects (51) as NPC is an ultra-rare orphan disorder. All sites use the same protocol, entry criteria, data collection methods, and endpoints and are monitored to verify compliance with the protocol. The NPC-SS will be assessed and scored centrally for all subjects across sites, and this blinded centralized scoring will be used for all NPC-SS efficacy analyses. According to Meinert (1986), these criteria justify pooling results across centers [4].

8.7.Stratification

Although randomization in Part B is stratified by miglustat use and baseline NPC-SS level to ensure balance across the 2 treatment groups, the statistical analyses will not be stratified

based on these variables. The number of subjects in any one stratum may be too small to

make any meaningful comparative inferences.

All formal statistical analyses will be stratified by whether the subject entered the study in Part

A or entered in Part B.

In order to understand the effects of stratification, the following stratification groups will be

used as sensitivity analyses:

Subjects randomized in Part A

• Subjects randomized in Part B, miglustat use +, NPC-SS total score ≥ 20

• Subjects randomized in Part B, miglustat use -, NPC-SS total score ≥ 20

Subjects randomized in Part B, miglustat use +, NPC-SS total score < 20

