The NPC-SS composite score is the sum of the ambulation, cognition, fine motor, and swallowing domains of the NPC-SS. This outcome ranges in value from 0 to 20 points at each assessment. Measurements at baseline, each post-baseline measurement through Week 52, and change from baseline for each measurement through Week 52 will be summarized descriptively. For the co-primary efficacy analysis, any missing Week 52 assessments will be imputed. Subjects who take the rescue option will be considered dropouts and will need to have their missing Week 52 assessment imputed. To protect against the potential bias that may occur if outcomes for the completers are different from those for the non-completers (i.e., missing not at random; MNAR), the approach taken will be to impute all missing observations from either treatment arm as if they came from the sham group. That is, the average change from baseline for the sham group will be added to the baseline observation of each subject with a missing assessment at Week 52. The missing value imputation will occur at the individual domain level. An ANCOVA, with treatment group, study part, and baseline NPC-SS composite score included in the model, will be performed to test for differences in the change from baseline to Week 52 between VTS-270 and sham groups in the co-primary efficacy outcome measure. Considering the small sample size, this ANCOVA will be performed using a nonparametric approach such that the outcome data will be ranked. Average ranks will be assigned in case of ties. The null hypothesis will be $H_0: \Delta_d - \Delta_s = 0$, and the alternative hypothesis will be H₁: Δ_d - $\Delta_s \neq 0$, where Δ_d is the mean rank of the change from baseline for the drug VTS-270 group and Δ_s is the mean rank of the change from baseline for the sham group. The null hypothesis will be tested with both means adjusted for study part in which the subject was randomized to (A or B) and baseline NPC-SS composite score. This test will be performed at α =0.05 level (two-sided) of significance.

August 27, 2018

Page 32

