The analysis of the blinded Clinician CGIC at Week 52 will be conducted using the nonparametric Van Elteren method to test for the treatment effect using study part as a blocking variable. Average ranks will be assigned when there are ties within a block. Missing Week 52 assessments will be imputed. To protect against the potential bias that may occur if outcomes for the completers are different from those for the non-completers (i.e., MNAR), the approach taken will be to impute all missing observations from either treatment arm as if they came from the sham group. That is, the average blinded Clinician-CGIC at Week 52 for the sham group will be imputed for each subject with a missing assessment at Week 52. Because the average value of the sham group used for imputation may not be an integer, but needs to be in order to fit the ordinal categories of the blinded Clinician-CGIC, the ceiling (worst case) will be applied to the average value before imputation.

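### SAP 12.6 treats a significant hearing-by-treatment interaction as evidence of unblinding bias, but that term cannot identify such bias, and the supplied text has no hearing-based check for the co-primary Clinician CGIC

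*SAP*

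**What the plan says.** SAP 12.6 accepts that the drug's known ototoxicity may threaten the blind. Its stated worry is that the site staff member scoring the NPC-SS "notices over the course of the study that the subject experiences clinical hearing impairment", and that this knowledge colours the score. Audiology results and recorded adverse events are withheld from that person, so the SAP uses a proxy. It reruns the ranked composite ANCOVA (treatment, study part, baseline) with a "variable indicating the recording of hearing impairment (AE or recommendation for hearing" aid) and that variable's interaction with treatment. A significant interaction (at the two-sided 0.05 level "of significance) will provide evidence that an unblinding bias has occurred". No reading is given for the hearing main effect, for a non-significant interaction, or for an interaction that cannot be estimated.

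On every efficacy analysis of this scale, SAP 8.6 states: "The NPC-SS will be assessed and scored centrally for all subjects across sites, and this blinded centralized scoring will be used".

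For the other co-primary, SAP 11.1 says: "The analysis of the blinded Clinician CGIC at Week 52 will be conducted using the nonparametric Van Elteren method". A footnote to Exhibit 2 has the blinded clinician meet the subject to form the CGIC baseline. Neither the five sensitivity analyses in 11.2 nor the subgroups in 11.7 use hearing. Under 11.3 both co-primaries must be rejected before key secondary testing.

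**The concern.** A rater who notices hearing loss but does not know the arm has no reason to treat an impaired sham subject differently from an impaired VTS-270 subject. Bias of that kind attaches to hearing status, not to the combination of hearing status and arm. It still reaches the treatment comparison, because an ototoxic drug puts more impaired subjects in the active arm. The interaction is therefore the wrong term for the scenario that 12.6 describes.

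The reverse error is also open: a larger true effect in subjects who develop hearing loss would be labelled bias.

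This is the only analysis in the supplied text aimed at the ototoxicity threat to blinding. If its rule misleads, so does any robustness statement built on it. The CGIC, whose rater sees the subject in person, is left unexamined.

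**Working it through.** **Inputs from SAP 8.5.** The split is "approximately 51 subjects: 16 on sham and 35 on active treatment"; "A common standard deviation of 1.64"; assumed mean changes 0.2 and 1.6 (difference 1.4); two-sided alpha 0.05; stated power 79%. The documents give no hearing rates, no bias size and no SD for the CGIC. All hearing rates and bias sizes below are assumptions.

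**1. The SAP's own figure.** SE = 1.64 × √(1/35 + 1/16) = 0.495. Noncentrality = 1.4/0.495 = 2.83. With 49 df the power is 0.792, which reproduces the stated 79%.

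**2. What the interaction can see.** Let a share pA of VTS-270 subjects and pS of sham subjects carry the hearing flag, and let flagged subjects be scored b points too favourably.

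- *Same bias in both arms.* Interaction contrast = (−b) − (−b) = 0. Treatment contrast is shifted by −b × (pA − pS). With b = 0.7 and rates of 70% and 10%, the shift is 0.7 × 0.60 = 0.42 points in favour of drug.
- *Bias only in flagged VTS-270 subjects.* Interaction contrast = −b.
- *No bias, true benefit e only in flagged VTS-270 subjects.* Interaction contrast = −e.

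The last two patterns give the same data when b = e, so no test on these data can separate them.

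**3. Power where the term does respond.** SE = 1.64 × √(sum of 1/cell size), noncentral t, df = 51 − 6 = 45, contrast 1.4 points, unranked:

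| VTS-270 flagged / not | Sham flagged / not | SE | Power |
|---|---|---|---|
| 18 / 17 | 1 / 15 | 1.78 | 12.0% |
| 18 / 17 | 2 / 14 | 1.36 | 17.2% |
| 18 / 17 | 4 / 12 | 1.10 | 23.9% |
| 17 / 18 | 8 / 8 (best case) | 0.99 | 28.3% |

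**4. Estimability.** With no flagged sham subject the interaction cannot be estimated. That chance is (1 − q)^16 = 44%, 19% and 3% at sham rates q of 5%, 10% and 20%.

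**5. Simulation with the ranked model.** 4,000 trials per setting; 35:16, with 9 and 3 from Part A; change drawn from N(1.6, 1.64), rounded to whole points, then ranked. No drug effect; 0.7-point bias for flagged subjects in both arms:

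| Flag rates, VTS-270 / sham | Planned test falsely favours drug (nominal 2.5%) | Hearing term significant, model without interaction |
|---|---|---|
| 50% / 5% | 8.0% | 22.4% |
| 50% / 30% | 4.0% | 28.6% |
| 70% / 10% | 11.7% | 20.9% |
| 90% / 5% | 20.0% | 11.6% |
| 90% / 30% | 11.8% | 16.8% |

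At 30% / 10% the false-favour rate is about 4%. The interaction is significant in about 3-5% of estimable trials, as it is with no bias. In the model with the hearing flag but no interaction, the treatment term falsely favours drug in only about 2-3%. So the model carries some of the signal, in terms that the SAP does not read.

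**6. Other patterns, 1.4 points.** Bias confined to flagged VTS-270 subjects makes the interaction significant in about 10-24% of estimable trials. A true benefit confined to the same subjects, with no bias, makes it significant in 7-23% of all trials, and the hearing term in 16-60%. Hence the hearing term is not diagnostic either.

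**The case against.** The best defence is that central blinded scoring (8.6), the withheld audiology and adverse event records, and a scale with concrete anchors such as wheelchair use or tube feeding all limit how far an NPC-SS score can drift. That stands. A reader might take a 1.4-point bias as the expected case: at assumed rates of 90% and 5% the planned test would then falsely favour drug in 59% of simulated trials. The documents do not support this. They give no hearing rates, and that bias would equal the whole planned effect.

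Second, the interaction is not useless. It reacts to bias confined to the active arm, and 12.6 speaks of evidence, not proof. This also stands, but the reaction is weak and a real effect produces the same pattern.

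Third, 12.6 already fits the needed model. In simulation the treatment term in that expanded model falsely favours drug in only 1.9-3.5% of trials. So the defect lies mainly in how the output is to be read.

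Fourth, a reader might say that 12.6 leaves open whose knowledge is at issue. It does not: it names site staff performing the NPC-SS. The gap is that 8.6 bases the efficacy analyses on central scores.

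Finally, the conversational signs of hearing loss in 12.1.1 are those reported to the adverse event assessor. The text does not say that the CGIC clinician observes them, and most of the protocol body was not supplied.

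**Conclusion.** The rule in 12.6 is wrong as written. The interaction stays at its null rate under the bias the section describes, cannot tell active-only bias from true effect modification, has at most 28% power for a 1.4-point contrast, and may not be estimable. The false-favour range of about 4-20% rests on an assumed 0.7-point bias and assumed flag rates of 30-90% (VTS-270) and 5-30% (sham), with the active rate the higher. With equal rates there is no inflation. Central scoring may make the true figure smaller.

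The missing CGIC check is a gap in the supplied text only. It cannot be quantified, because no CGIC SD is given.

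A reader might infer that the blind has failed or that the primary result is biased. Nothing in the documents shows either. No primary test, alpha or stated power changes; what changes is the robustness conclusion that can be drawn. The correction should be made. Confidence is medium, because the size depends on assumed rates.

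**What to change.** 1. Replace the inference sentence in 12.6 with: *The interaction is descriptive; a significant result is compatible with unblinding bias or with a true difference in effect, and a non-significant or non-estimable result does not exclude bias.*
2. Report, with confidence intervals and both ranked and unranked, the hearing term and the treatment effect from the models with and without the interaction. Note that hearing status arises after randomisation and is affected by treatment. Name the model without interaction as the one to report if the interaction cannot be estimated.
3. Add a parallel descriptive analysis for the Clinician CGIC, for example its distribution by arm and hearing flag, plus a ranked model with treatment, study part and hearing flag.
4. Reconcile 12.6, which is concerned with site staff performing the NPC-SS, with 8.6, which uses blinded central scoring.

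Optional: a simple tipping-point analysis that worsens the scores of subjects with a recorded hearing event, kept within the scale range and labelled as neither proving nor excluding bias. It does not identify bias either: a genuine benefit can also tip early.

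Cost: SAP wording and a little programming, with no new data. The downside is a possibly less favourable robustness statement.
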